4.1.3. RADIATION THERAPY

4.1.3.1.Dose specifications/escalation

SRS will be delivered in 3 fractions. Provided that the MTD has not been reached, the total dose will be increased in 3 Gy increments:

Dose Level	Dose Per Fraction	Total Dose
1	8 Gy	24 Gy
2	9 Gy	27 Gy
3	10 Gy	30 Gy
4	11 Gy	33 Gy

A minimum of six patients will be enrolled per arm:

Arm	
1	4.2 - 14.1 cm ³ brain metastasis following surgical resection
2	14.2 - 33.5 cm ³ brain metastasis following surgical resection

Similar to RTOG 90-05, the dose limiting toxicity (DLT) is defined as grade 3, 4, or 5 RTOG central nervous system (CNS) acute radiation morbidity scoring criteria (Appendix C) observed within 30 days of radiosurgery. The MTD is defined as one dose level below the highest toxic dose (i.e., the DLT dose).

The occurrence of late toxicities will be continuously monitored. If a late DLT occurs in 3 or more out of 6 (or 4 or more out of 12) patients at a certain dose level after the radiation dose had already been escalated to the next level, the MTD will be backtracked to the level

below the one at which the DLTs occurred.

Number of Patients at a Given	Escalation Decision Rule					
Dose Level with a DLT						
0-1 out of 6	Enter 6 patients at the next higher dose level					
2 out of 6	Enter at least 6 more patients at the current dose level.					
	• If 0-1 of these 6 experience a DLT (i.e., 2-3					
	out of 12), then proceed to next dose level.					
	• If 2 or more of these 6 experience a DLT (4 or more out of 12), then dose escalation will be stopped. Six additional patients will be entered at the next lower dose level if only 6 patients were previously entered.					
3 or more out of 6	Dose escalation will be stopped. Six additional patients will be entered at the next lower dose level if only 6 patients were previously entered.					

Does escalation will proceed as follows, with minimum waiting period of 30 days before proceeding with the next higher dose level:

Should a patient not be evaluable at 30 days (due to death or loss to follow-up or discontinuation of the protocol follow-up per patient preference), then additional patients may be enrolled on each arm such that at least 5 of 6 are evaluable and experience no DLT. For example, should one patient be lost to follow up, but the remaining 5 patients have no DLT, then dose escalation may proceed.

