4.5 Criteria for Removal from Study

- Disease progression or death
- Intercurrent illness that prevents further administration of treatment: a condition, injury, or disease unrelated to cancer, that renders continuing of radiation treatment unsafe or regular study visits impossible.
- Unacceptable adverse event(s) (see adverse events)
- Patient decides to withdraw from the study
- General or specific changes in the patient's condition that render the patient ineligible for the study
- Non-compliance with protocol-required evaluations and study visits
- Inability of subject to comply with study requirements
- Determination by the investigator that it is no longer safe for the subject to continue therapy
- Patients who inadvertently become pregnant
- At the discretion of the treating investigators

Subjects who are discontinued from the study will still be followed for disease progression and survival.

Subjects who discontinue should, if possible, be seen and assessed by an investigator(s). The reason for withdrawal and the date of withdrawal must be documented.

If the reason for withdrawal from the trial is the death of the subject, the two options for categorizing withdrawal are either progressive disease or an adverse event (AE; more than one AE may be documented as a reason for withdrawal). Only one event will be captured as the cause of death. Note that death is an outcome and not an AE.

All trial treatment-related toxicities and serious adverse events (SAEs) must be followed up until resolution.

At withdrawal, all on-going study-related toxicities and SAEs must be followed until resolution, unless in the investigator's opinion, the condition is unlikely to resolve due to the subject's underlying disease.

Subjects/patients who discontinue from the study for reasons unrelated to the study (e.g., personal reasons, or adverse events after registration but prior to receiving study therapy) may be replaced as required for the study to meet its objectives. The decision

to remove a subject/patient and to replace dropouts will be made by the treating investigator. The replacement will generally receive the same treatment or treatment sequence (as appropriate) as the allocation number replaced.

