12.3 Sample Size

12.3.1 Accrual estimates

Six subjects per group will be enrolled at the starting dose for each of the four arms. Should a patient not be evaluable at 30 days (due to death or loss to follow-up or discontinuation of the protocol follow-up per patient preference), then additional patients may be enrolled on each arm such that at least 5 of 6 experience no DLT. The maximum number of subjects per arm will depend on the number of dose levels reached. If all four dose levels are reached, the maximum number of evaluable subjects in each arm is 30. If all four dose levels are reached for the all two arms of the study, the maximum number of subjects for the entire study is 60.

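### The rule for patients who leave before day 30 makes no exception for a prior DLT, disagrees with section 4.5, and read literally can take a DLT out of the escalation count

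*Combined protocol and SAP*

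**What the plan says.** **The evaluability route (4.1.3.1, repeated in 11.2).** The clause opens "Should a patient not be evaluable at 30 days (due to death or loss to follow-up" and adds stopping follow-up by patient preference. The consequence is that "additional patients may be enrolled on each arm such that at least 5 of 6 are evaluable and experience no DLT". An example follows: "should one patient be lost to follow up, but the remaining 5 patients have no DLT, then dose escalation may proceed". Section 12.3.1 repeats the clause for accrual with a shorter target: "additional patients may be enrolled on each arm such that at least 5 of 6 experience no DLT". None of the three sections mentions a patient who had a DLT before leaving, and none caps the number of additional patients.

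**The withdrawal route (4.5).** Replacement is open to those who "discontinue from the study for reasons unrelated to the study". The two examples are personal reasons and an adverse event that precedes study therapy. The decision "to remove a subject/patient and to replace dropouts will be made by the treating investigator". The grounds for removal include an unacceptable adverse event and the discretion of the treating investigators.

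**What counts as a DLT.** Sections 4.1.3.1, 10.2 and 11.2 define it as grade 3, 4 or 5 on the RTOG acute CNS scale, seen within 30 days of radiosurgery. In Appendix C, grade 3 is neurologic findings that need hospitalisation for initial management, and grade 5 is death, with no cause specified.

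**What the count decides.** With 0-1 DLTs in 6 the dose goes up. With 2 in 6 the level is expanded by six: 2-3 in 12 escalates and 4 or more in 12 stops. With 3 or more in 6 escalation stops. The MTD, the primary endpoint, follows from these decisions.

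**The concern.** A DLT rule needs one definition of who is counted, fixed before outcomes are known. Here there are two, with different criteria, and the one placed beside the decision table does not say that a DLT already seen stays in. The clause also ties additional enrolment to an outcome (patients without a DLT) and not to a complete cohort. Section 4.5 leaves removal and replacement to someone who knows the patient's toxicity.

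If a patient with a DLT is treated as not evaluable and another is enrolled, the event leaves the numerator and the patient leaves the denominator. The observed DLT rate falls, and the next cohort may be treated at a dose that the full count would not have allowed. The shortest wait before escalation is 30 days (4.1.3.1), and section 11.1 schedules no independent check of the count before a dose increase.

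**Working it through.** **1. The plan's own thresholds.** Two DLTs in the first six plus 0-1 in the next six gives 2-3 of 12. Two plus two or more gives 4 or more of 12. Both cut-offs reproduce. The plan states no target DLT rate and no error rate for the escalation rule, so there is no operating figure to reproduce.

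**2. The passages applied to three patients treated at the current level.**

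| Patient | 4.1.3.1, 11.2, 12.3.1 | 4.5 | DLT definition |
|---|---|---|---|
| Dies within 30 days | Not evaluable; additional patient allowed | Replaceable only if unrelated to the study | Grade 5 on the scale, so a DLT |
| Hospitalised for neurologic findings on day 10, then stops follow-up because of it | Not evaluable if the preference clause is applied literally | Not replaceable, as the reason is study-related | Grade 3, already observed, so a DLT |
| Leaves without a DLT for personal reasons | Not evaluable; additional patient allowed | Replaceable | No DLT seen |

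The routes agree only in the third row. In the first, the text puts one event in both categories. In the second, it is silent on which provision prevails.

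**3. The plan's example.** One patient is lost and five have no DLT. Counting the lost patient as a DLT gives 1/6, which still escalates. The example is harmless.

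**4. Cohorts where one patient decides.**
- 2/6 (expand): one DLT patient is replaced by a patient without a DLT, giving 1/6 (escalate). Five of six are then DLT-free, which is exactly the stated target.
- 3/6 (stop): one DLT patient is replaced by a patient without a DLT, giving 2/6 (expand). Only four of six are DLT-free, so this does not meet the 5-of-6 target. It needs the not-evaluable label to be applied regardless of that target.

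**5. Illustration of size.** Assumptions, neither in the documents: true DLT probability p, and a share q of DLT patients who are classed as not evaluable and replaced until six are counted. Per treated patient, the chance of being counted is 1 − pq and the chance of being counted with a DLT is p(1 − q). Hence

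p' = p(1 − q)/(1 − pq).

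With X and Y binomial(6, p'),

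P(escalate) = P(X ≤ 1) + P(X = 2) × P(Y ≤ 1).

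At p = 0.40 and q = 0: P(X ≤ 1) = 0.0467 + 0.1866 = 0.2333 and P(X = 2) = 0.3110, so P(escalate) = 0.2333 + 0.3110 × 0.2333 = 0.306. At q = 0.1, p' = 0.36/0.96 = 0.375. At q = 0.25, p' = 0.30/0.90 = 0.333.

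| p | q = 0 | q = 0.1 | q = 0.25 |
|---|---|---|---|
| 0.20 | 0.816 | 0.852 | 0.900 |
| 0.30 | 0.556 | 0.616 | 0.710 |
| 0.40 | 0.306 | 0.362 | 0.467 |
| 0.50 | 0.135 | 0.171 | 0.248 |

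**The case against.** The strongest reply is that the plan never tells anyone to discard an observed DLT. A DLT is an event seen within 30 days, and the table counts patients with one. A patient hospitalised on day 10 meets both conditions, and not evaluable most naturally means that DLT status is unknown. On that reading q is zero for living patients and the table above shows no effect. This stands as the better reading. It does not remove the ambiguity, because the clause that follows the table has no exception for a known DLT. It also does not reach death, which the clause names outright. The clause may have been meant for deaths from other causes, but neither it nor Appendix C draws that line.

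Second, personal reasons in 4.5 and patient preference in 4.1.3.1 may be meant as one category, and 4.5 requires the reason and date of withdrawal to be documented. That narrows the conflict to exits driven by toxicity but recorded as preference, and to deaths.

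Third, there are safeguards. Toxicities and SAEs are followed to resolution, with an exception at withdrawal for conditions judged unlikely to resolve because of underlying disease. Patients who cannot attend are reached by phone or through local records. AEs go to the safety coordinator within 10 working days, and the DSMC is independent of the investigators. These make it likely that the event is recorded. None says how it counts for escalation.

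A reader might infer that neither route keeps a patient with a DLT. The documents do not support that: 4.5 on its face bars replacing someone who leaves because of treatment toxicity. A reader might also infer that patients with DLTs are the ones most likely to leave, or extend the illustration to q = 0.5, where P(escalate) at p = 0.40 reaches 0.692. The documents give no basis for the first, and the second supposes that half of all DLT patients leave and are struck from the count.

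**Conclusion.** The concern holds as a conflict between passages on a rule that drives the primary endpoint. It is explicit for a death within 30 days and a matter of ambiguity for a living patient who has a DLT and then stops follow-up. One patient is enough to turn 2/6 into 1/6, and 3/6 into 2/6 on the looser reading. A single non-evaluable patient in a cohort with no other DLT cannot change the decision.

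The probabilities (31%, 36% and 47% at p = 0.40 for q = 0, 0.1 and 0.25) rest wholly on assumed p and q. They show how sensitive the rule is and are not evidence of a bias that has occurred. It is tempting to say that the plan deletes DLTs; what the text supports is that it does not prevent this.

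**What to change.** Reconcile 4.1.3.1, 4.5, 11.2, 12.3.1 and Appendix C into one counting rule:

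1. Any treated patient with a DLT observed within 30 days, including a death that meets the DLT definition, stays in numerator and denominator whatever happens later. Say how a death within 30 days is classed against that definition, and by whom.
2. Only patients who leave before day 30 without a DLT are not evaluable and may be replaced. Record the reason. Replacement follows this rule and not case-by-case discretion.
3. In 4.1.3.1, 11.2 and 12.3.1, state the replacement target as a complete cohort of evaluable patients, to which the existing decision table is then applied. Keep the stated exception for five evaluable patients with no DLT.

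Adding the word on evaluability back into 12.3.1 would not be enough, because the outcome-based target is also in 4.1.3.1 and 11.2. Asking the principal investigator to confirm each replacement would not be enough either, because nothing shows that this role is separate from the treating investigators.

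The cost is wording in four sections and a cross-reference to Appendix C, with no patients beyond those the present clause already allows. The downside is that escalation may stop earlier in cohorts where a patient with a DLT leaves.

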4.6 Alternatives

Alternative treatments include conventional fractionated whole brain radiotherapy, stereotactic radiosurgery alone, systemic therapy, or no therapy.

4.7 **Compensation**

Subjects will not be paid for their participation in the study.

5. INVESTIGATIONAL AGENT/DEVICE/PROCEDURE INFORMATION

5.1 **Investigational Agent/Device/Procedure**

N/A

5.2 Availability

N/A

5.3 Agent Ordering

N/A

5.4 Agent Accountability

N/A

6. DOSING DELAYS/DOSE MODIFICATIONS

N/A

7. ADVERSE EVENTS AND REPORTING PROCEDURES

7.1 **Potential Adverse Events**

- 7.1.1. Early, < 30 days from treatment: Expected adverse events include fatigue, headache, neck pain, nausea and vomiting, and lethargy.
- 7.1.2. Late, > 30 days from treatment: Possible adverse events include focal neurologic deficits, memory difficulties, dementia, radiation necrosis, and radiation induced neoplasm.

7.2 Adverse Event Reporting

In the event of an adverse event the first concern will be for the safety of the subject. Appropriate medical, psychological and/or supportive intervention should be initiated as soon as possible. All subjects/patients with serious adverse experiences must be followed up for outcome.

7.2.1. Definition:

- 7.2.1.1.**Definition of adverse event:** any unfavorable and unintended sign, symptom, or disease temporally associated with the use of a medical treatment or procedure regardless of whether it is considered related to the medical treatment or procedure (attribution of unrelated, unlikely, possible, probable, or definite).
- 7.2.1.2. **Definition of serious adverse event:** any adverse experience that results in any of the following outcome: death, a life-threatening experience, inpatient hospitalization or prolongation of existing hospitalization, a persistent or significant disability/incapacity, or a congenital anomaly/birth defect. Important medical events that may not result in death, be life threatening, or require hospitalization may be considered a serious adverse event when, based upon medical judgment, they may jeopardize the patient or subject and may require medical or surgical intervention to prevent one of the outcomes listed in this definition.
- 7.2.1.3. **Definition of unanticipated problems involving risks to participants or others (UPs):** events (including internal or external events, death, lifethreatening experiences, injuries, breaches of confidentiality, or other problems) that occur any time during or after the research study, which in the opinion of the PD are:
- 7.2.1.4.Unexpected not in the consent form, protocol, package insert, or label; or unexpected in its frequency, severity, or specificity, AND
- 7.2.1.5.Related to the research procedures caused by, or probably caused by research activity, or, if a device is involved, probably caused by , or associated with the device, AND
- 7.2.1.6.Harmful caused harm to participants or others, or placed them at increased risk of harm (including physical, psychological, economic, or social harm.

- 7.2.1.7.**Definition of reportable information:** New information that indicates a change to the risks or potential benefits of the research, in terms of severity or frequency.
 - **7.2.1.7.1.** Protocol deviation or violation, only if:
 - 7.2.1.7.1.1.Intended to eliminate apparent immediate hazard to a research participant, or
 - 7.2.1.7.1.2.Harmful (caused harm to participants or to others, or placed them at increased risk of harm including physical, psychological, economic, or social harm), or
 - **7.2.1.7.1.3.**Possible serious or continued noncompliance
 - **7.2.1.7.2.** Complaint that is unresolved by the research team, or that indicates increased or unexpected risks.
 - **7.2.1.7.3.** Incarceration when in the opinion of the PD it is in the best interest of the participant to remain on the study.
- 7.2.1.8.**Unanticipated adverse device effect.** New information about the effect on health or safety or any life-threatening problem or death caused by, or associated with, a device, if that effect, problem, or death was not previously identified in nature, severity, or degree of incidence, or any other unanticipated serious problem associated with a device that relates to the rights, safety, or welfare or subjects.

Changes resulting from normal growth and development which do not vary significantly in frequency or severity from expected levels are not to be considered adverse experiences. Examples of this may include, but are not limited to, teething, typical crying in infants and children, and onset of menses or menopause occurring at a physiologically appropriate time.

If disease progression is noted during a protocol-specified reevaluation of the status of a patient's cancer, and the progression is manifested solely by results of tumor markers and/or radiologic imaging, that occurrence of progressive disease will NOT be recorded as an adverse experience.

7.2.2. Adverse Event Reporting

7.2.2.1.PIs or designees should report AEs, whether considered treatment related or not, to the CCTO Safety Coordinator per protocol and regulatory timeframes.

Events should be reported within 10 working days of becoming aware of the event (5 days if the event is life-threatening or resulted in death).

- 7.2.2.2.Unanticipated adverse device effects should be reported to FDA, CCTO and participating investigators within 10 working days of becoming aware of the event (5 days if the event is life threatening or resulted in death).
- 7.2.2.3. RTOG central nervous system (CNS) acute radiation morbidity scoring criteria (Appendix C) will be used to grade acute CNS toxicity.
- 7.2.2.4. The Common Terminology Criteria for Adverse Events (CTCAE) version 4.0 will be used for grading of adverse events (Appendix E).

8. CORRELATIVE/SPECIAL STUDIES

- 8.1.Dose heterogeneity and conformality within the target volume will be calculated for each lesion to investigate whether these factors have any correlation to local control or toxicity.
- 8.2.To identify potential predictors of response, the following pre-treatment tumor characteristics will be collected:
 - 8.2.1. Lesion size
 - 8.2.2. Histology
 - 8.2.3. Pattern of enhancement on MRI scan
 - 8.2.4. Presence or absence of extensive edema

9. STUDY CALENDAR

Parameters	Pre-	1 month ^a	3 month ^b	6 month ^b	9 month ^b	12 month ^b
	Entry					
History/	Х	Х	Х	Х	Х	Х
Physical Exam						
KPS	Х	Х	Х	Х	Х	Х
MRI	Х		Х	Х	Х	Х
Steroid use	Х	Х	Х	Х	Х	Х
Assessment						
Toxicity		Х	Х	Х	Х	Х
Evaluation						
QOL Evaluation	Х	Х	Х	Х	Х	Х

^a time point \pm 7 days

^b time point \pm 14 days

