4.2 General Concomitant Medication and Supportive Care Guidelines

Supportive treatment may include anti-emetics, anti-diarrheal medications, antipyretics, anti-histamines, analgesics, antibiotics, and others, such as blood products. Patients will be permitted to receive appropriate supportive care measures as deemed necessary by the treating physician.

Steroids may be given after each SRS treatment to decrease the risk of CNS symptoms due to cerebral edema. In addition, steroids may be used as required to control CNS symptoms due to tumor-associated or RT-associated cerebral edema, but wherever possible, should be tapered and stopped.

Nausea/vomiting: Nausea and vomiting should be treated aggressively. In particular, the use of antiemetics including 5HT3 antagonists and/or dexamethasone is encouraged. Patients should be strongly encouraged to maintain liberal oral fluid intake during therapy.

4.3 **Duration of Therapy**

SRS will be given in 3 fractions, each approximately 24 hours apart.

4.4 **Duration of Follow Up**

Follow-up schedule is summarized in section 9. Study Calendar.

Patients will be seen in follow-up at 1st, 3rd, 6th, 9th, and 12th months following radiation. The following will be obtained at pre-treatment evaluation and at each follow-up time point: Neurologic history and physical examination, KPS, steroid use assessment, and toxicity evaluation. MRI with gadolinium will be obtained at pre-treatment and at 3, 6, 9, and 12 months following treatment until progression is documented and continuing every 3 months for those without evidence of intracranial progression.

After the first 12 months, patients will be followed every 3-6 months at the discretion of the patient's physician. At each visit, interval history, physical exam, KPS, toxicity evaluation, and brain MRI scans will be obtained.

For those subjects who are unable to come for clinic visits, clinical follow-up information will be obtained via 1) a phone call to the patient and/or 2) clinic source document from his/her local physician. For subjects unable to appear in person for clinic visits, HRQOL questionnaires will be completed via a telephone interview or mail.

For patients unable to return for imaging studies, source documents from outside institutions will be used to document imaging follow-up.

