10.2 Other Response Parameters

The primary endpoint of this study is to determine the MTD of tri-fraction SRS. The MTD is defined as one dose level below the highest toxic dose (i.e., the DLT dose). Similar to RTOG 90-05, the dose limiting toxicity (DLT) is defined as grade 3, 4, or 5 RTOG central nervous system (CNS) acute radiation morbidity scoring criteria (Appendix C) observed within 30 days of radiosurgery.

The occurrence of late toxicities will be continuously monitored. If a late DLT occurs in 3 or more out of 6 (or 4 or more out of 12) patients at a certain dose level after the radiation dose had already been escalated to the next level, the MTD will be backtracked to the level

below the one at which the DLTs occurred.

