11. DATA REPORTING / REGULATORY CONSIDERATIONS

11.1 Monitoring plan

Stanford Cancer Center (SCC) Data and Safety Monitoring Committee (DSMC) will be responsible for monitoring the research yearly and will operate independently from the clinical investigators. The primary responsibility of the DSMC is to review the reported study data to confirm it is accurate, complete, and verifiable from source documents. The DSMC will also confirm that the conduct of the trial maintains the safety and well being of human subjects, and is in compliance with the currently approved protocol, with GCP, and with applicable regulatory requirements. Study safety data will be reviewed by the DSMC in the form of summary reports or data listings on a regular basis.

11.2 Stopping rules (for the individual patient and for the study as a whole)

The dose limiting toxicity (DLT) is defined as grade 3, 4, or 5 RTOG central nervous system (CNS) acute radiation morbidity scoring criteria (Appendix C) observed within 30 days of radiosurgery.

The occurrence of late toxicities will be continuously monitored. If a late DLT occurs in 3 or more out of 6 (or 4 or more out of 12) patients at a certain dose level after the radiation dose had already been escalated to the next level, the MTD will be backtracked to the level below the one at which the DLTs occurred.

Number of Patients at a Given Dose Level with a DLT	Escalation Decision Rule
0-1 out of 6	Enter 6 patients at the next higher dose level
2 out of 6	 Enter at least 6 more patients at the current dose level. If 0-1 of these 6 experience a DLT (i.e., 2-3 out of 12), then proceed to next dose level. If 2 or more of these 6 experience a DLT (4 or more out of 12), then dose escalation will be stopped. Six additional patients will be entered at the next lower dose level if only 6 patients were previously entered.

Does escalation will proceed as follows:

3 or more out of 6	Dose escalation will be stopped. Six additional
	patients will be entered at the next lower dose level if
	only 6 patients were previously entered.

Should a patient not be evaluable at 30 days (due to death or loss to follow-up or discontinuation of the protocol follow-up per patient preference), then additional patients may be enrolled on each arm such that at least 5 of 6 are evaluable and experience no DLT. For example, should one patient be lost to follow up, but the remaining 5 patients have no DLT, then dose escalation may proceed.

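### The 1-month toxicity visit may fall on about day 23 and no contact on or after day 30 is required, so the last week of the 30-day DLT period can lack a scheduled assessment when escalation is decided

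*Combined protocol and SAP*

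**What the plan says.** - **DLT period.** Sections 4.1.3.1, 10.2 and 11.2 define a DLT as a grade 3 to 5 event on the RTOG acute CNS scale "observed within 30 days of radiosurgery".
- **Visits.** Section 4.4 states: "Patients will be seen in follow-up at 1st, 3rd, 6th, 9th, and 12th months following radiation". In the Section 9 calendar, toxicity evaluation is marked at each of these visits. Footnote a gives the 1-month visit a window of "time point \pm 7 days". Footnote b gives the later visits "time point \pm 14 days".
- **Escalation timing.** Section 4.1.3.1 introduces the decision table "with minimum waiting period of 30 days before proceeding with the next higher dose level". It does not say from which patient, fraction or date the wait runs. Section 11.2 repeats the table after only "Does escalation will proceed as follows", without the wait.
- **Evaluability.** Sections 4.1.3.1 and 11.2 both contain a rule that begins "Should a patient not be evaluable at 30 days". The reasons listed for not being evaluable are death, loss to follow-up and the patient's choice to stop follow-up.
- **Reporting between visits.** Section 7.2.2 requires adverse events to be reported within 10 working days of awareness, or 5 days if life-threatening or fatal.

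**The concern.** The MTD is the primary endpoint and is read from DLT counts in cohorts of 6 or 12. In a cohort of six, one event can change the decision: 1 against 2 DLTs separates escalation from expansion, and 2 against 3 separates expansion from stopping.

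The assessment window and the DLT period do not match. A patient seen on day 23 has complied with the calendar, yet days 24 to 30 are then covered by no scheduled assessment. The 30-day wait lets the time pass but does not prescribe another look at the patient. The evaluability rule does not close the gap either: a patient seen on day 23 who is alive and still on study meets none of the listed reasons for being non-evaluable, and no text makes a day-30 contact a condition of being evaluable.

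The possible error runs one way. A DLT that is not known at the decision can only lower the count, and so can only favour escalation.

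**Working it through.** The documents give no figure on this point to reproduce. They state no expected DLT rate and no distribution of onset times, so the escalation probabilities below are illustrations on stated assumptions.

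**Step 1: calendar.** The inputs are the two footnotes of Section 9 and the 30-day DLT period.
- Earliest 1-month visit, taking a month as 30 days: 30 − 7 = day 23. For months of 28 to 31 days it is day 21 to 24.
- Part of the DLT period left after that visit: 30 − 23 = 7 days (range 6 to 9).
- Earliest next scheduled visit: 90 − 14 = day 76.

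**Step 2: escalation rule** (table in Sections 4.1.3.1 and 11.2). Escalate on 0 or 1 of 6. On 2 of 6, add six patients and escalate if 0 or 1 of those six has a DLT. With p the probability that a patient has a DLT that is counted:

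P(escalate) = A + B × A, where A = P(0 or 1 of 6) and B = P(2 of 6), both binomial.

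With full capture:
- p = 0.30: A = 0.420, B = 0.324, so 0.420 + 0.324 × 0.420 = 0.556.
- p = 0.40: A = 0.233, B = 0.311, so 0.233 + 0.311 × 0.233 = 0.306.

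**Step 3: share of DLTs missed.** Assume that onset is uniform over 30 days and that nothing is learned except at the visit.
- Visits spread evenly over days 23 to 37: visits on days 23 to 29 leave 7, 6, 5, 4, 3, 2 and 1 days unseen, and the other eight visit days leave none. Missed share = 28 / (15 × 30) = 0.062.
- Every visit on day 23 (extreme bound): missed share = 7/30 = 0.233.

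**Step 4: effect on escalation.** Replace p by p × (1 − missed share).

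| True DLT rate | Full capture | Visits spread over days 23–37 (6.2% missed) | Every visit on day 23 (23.3% missed) |
|---|---|---|---|
| 0.30 | 0.556 | counted rate 0.281: 0.461 + 0.317 × 0.461 = 0.607 | counted rate 0.230: 0.582 + 0.279 × 0.582 = 0.744 |
| 0.40 | 0.306 | counted rate 0.375: 0.274 + 0.322 × 0.274 = 0.362 | counted rate 0.307: 0.406 + 0.326 × 0.406 = 0.538 |

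Both right-hand columns assume no reporting between visits. Any such reporting moves them back towards the full-capture column, and complete reporting makes the effect zero.

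**The case against.** A reader might infer that the DLT count can be closed on day 23, or that a patient seen then is finally scored as free of DLT. The documents do not support this. Section 4.1.3.1 bars the next dose level for at least 30 days and judges evaluability at 30 days. No text makes the 1-month visit the only source of DLT status, and the DLT is defined by events in the period, not by findings at a visit.

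Three further points favour the plan:
- **These events are hard to overlook.** Appendix C sets grade 3 at neurologic findings that need hospitalization, grade 4 at paralysis, coma or frequent seizures, and grade 5 at death. Hospitalization and death are serious adverse events under Section 7.2.1, and Section 7.2.2 makes adverse events reportable on awareness whether related or not. Capturing almost none of them is implausible.
- **Patients who cannot attend are provided for.** Section 4.4 specifies a telephone call, local-physician records, or both.
- **A missed event may only be delayed.** The 3-month visit repeats the history and the toxicity evaluation, so an admission on days 24 to 30 can still be found and dated.

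These points stand against any large effect, but they do not close the gap. The reporting clock starts at awareness and creates no contact, so an admission elsewhere may not be known by the decision date. Recovery at 3 months may come after escalation. Section 10.1.1 classes toxicity observed after 30 days as late, so a day-27 event first learned of at month 3 could, read literally, fall under the late rule, which acts only at 3 or more of 6 or 4 or more of 12. No text says that such an event is added back to the acute count.

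**Conclusion.** The gap is real and documented: the scheduled assessment can precede the end of the DLT period by about a week, and nothing requires DLT status to be confirmed at or after day 30. The possible error favours escalation and touches the primary endpoint.

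Its size is uncertain. It runs from zero with full capture between visits, through a rise of about 0.05 in the probability of escalating with evenly spread visits and no other reporting, to a bound of about 0.19 (at a true rate of 30%) or 0.23 (at 40%) if every visit falls on day 23. That bound should not be read as the expected effect. It needs uniform onset, every visit at the earliest date and no outside reporting of events that involve hospitalization or worse, and the documents support none of these. Nor do the figures show that the final MTD will be too high, since late-learned events may be recovered before it is declared.

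Severity is minor to moderate. Confidence is high for the gap and low for its size.

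**What to change.** Make one of two changes:
- For the 1-month toxicity evaluation, change footnote a of Section 9 to −0/+7 days, that is, day 30 to 37.
- Keep the present window, but require a documented DLT-status contact on or after day 30 before a patient counts as evaluable for escalation. The telephone route in Section 4.4 is enough.

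Either change reduces the unassessed part of the DLT period from 7 days to 0, with no change to the dose levels, the DLT definition or the decision table. The cost is a narrower visit window in the first case and one call per patient seen early in the second.

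In the same edit, state from which patient and date the 30-day wait runs, reconcile Section 11.2 with Section 4.1.3.1 on whether the wait applies, and say that a DLT is classified by its onset date even if it is learned of later.
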